### 4. SELECTION AND ENROLLMENT OF SUBJECTS

#### 4.1 Inclusion Criteria

4.1.1 Adults ages 18 years and older

4.1.2 Deficient band ( $\leq 3$  mm) of keratinized mucosa.

4.1.3 Surgery to increase width of keratinized mucosa is clinically indicated or requested by the patient to facilitate oral hygiene procedures or to improve esthetics.

- 4.1.4 Patients must be able to understand and provide informed consent for participation in the protocol.
- 4.1.5 Patients in need of a graft measuring up to approximately 15 x 10 x 20 mm in dimension.
- 4.1.6 Women who test negative on a urine pregnancy test.

#### 4.2 Exclusion Criteria

- 4.1.1. Subjects with a known sensitivity to agents used in AlloPatch® production including: Gentamicin, Cefoxitin, Lincomycin, Polymyxin B, and Vancomycin
- 4.1.2. Subjects with potential medical complications such as evidence of clinically significant (as defined by investigators) renal, hepatic, cardiac, endocrine, hematologic, autoimmune, or any systemic disease which may complicate execution of the protocol and/or interpretation of results, i.e. interfere with wound healing or be a poor candidate for general anesthesia, uncontrolled diabetic, renal failure etc.
- 4.1.3. Documented history of syphilis, HIV, Hepatitis B or C virus
- 4.1.4. Pregnant women or women planning to become pregnant or unwilling to abstain or use double barrier contraceptives during the course of the study
- 4.1.5. Known or suspected allergy to bovine (cow) protein or iodine
- 4.1.6. Current radiation therapy or history of radiation therapy treatment to the intraoral donor biopsy site or recipient site for graft placement.
- 4.1.7. Smoking or use of tobacco products within 6 months prior to screening (subjects who quit smoking > 6 months prior to screening will be considered former smokers)
- 4.1.8. History of either alcohol or drug abuse in the past 5 years
- 4.1.9. Participation in another clinical trial within 30 days of screening
- 4.1.10. Subjects taking medications that can result in gingival enlargement/overgrowth (Cyclosporine, Dilantin, calcium channel blockers)
- 4.1.11. Current use of a medication used to treat a thyroid disease.
- 4.1.12. Current use of intravenous anti-resorptive therapies or a history of intravenous antiresorptive therapies during the past 5 years
- 4.1.13. Prior successful or attempted graft placement at the study defect site
- 4.1.14. Any physical or mental condition which in the opinion of the Investigator or Medical Monitor may interfere with the subject's ability to comply with the study procedures

### 4.3 Study Enrollment Procedures

The clinical treatment site will maintain a screening and enrollment log to track screen failures and enrollment (See Appendix A). A subject will not be screened until an Informed Consent Form has been signed. A subject's reason for ineligibility and reasons for nonparticipation or withdrawal from the study will be documented for inclusion in the Trial Master File (TMF).

Subjects who appear to meet the criteria for study participation will be informed of the study and, if interested, will review the study consent(s) with a qualified individual (approved by the PI to administer consent and listed on the Delegation of Authority Log).

During the informed consent process, study staff will detail the study procedures to ensure that the subject understands the study procedures and what is involved prior to signing the informed consent document. Subjects will be informed that they can withdraw from the study at any time and receive alternative care outside of the study. Subjects will be afforded as much time as needed to make an informed decision regarding willingness to participate in the study. Additionally, the study staff will provide contact information and will be available to discuss any questions or concerns potential subjects may have.

At the time of enrollment, immediately after written informed consent is obtained and before performing any study-related procedures, each subject will be assigned a unique sequential subject number for identification throughout the study by the study staff. This subject number will not be reused for any other participant in the study.

Once a subject has successfully met all inclusion and exclusion criteria, the subject will be randomized using the random number generator in a 1:1 ratio to EVPOME or POM via the web-based Treatment Assignment Tool U-M (TATUM) to obtain the subject's treatment assignment. The randomization schedule will begin with block sizes of 2, 4, or 6.

Upon randomization, an email will be sent to the Co-Investigator and/or any appropriate study staff. Randomization numbers will be assigned in the order in which subjects qualify for treatment, not in the order of study enrollment.

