### 3. STUDY DESIGN

This safety and efficacy study will be a single site, randomized, parallel-group autogenous ex vivo produced oral mucosa equivalent (EVPOME) vs. the “gold standard” palatal oral mucosa (POM), in subjects requiring additional keratinized oral mucosa.

A total of sixty subjects will be randomized in a 1:1 ratio to autogeneous EVPOME vs. POM. If randomized to EVPOME, the subjects will be scheduled for a harvest biopsy (Visit 2 procedure). If randomized to the POM group, the subjects will be scheduled for the graft (Visit 3 procedure). See Table 1(Section 6.1) for the Schedule of Evaluations. Subjects will be non-smoking adults (18 years and older) needing increased keratinized oral mucosa.

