6.1 Schedule of Evaluations

Procedure	Visit 1 Screening	Visit 2 Harvest Biopsy	Visit 3 Base- line Intra-oral Graft	Visit 4 Post- Op	Visit 5 Follow-up	Visit 6 Biopsy and Follow-up	Visit 7 Follow-up	Visit 8 End of Study
Timeline (in reference to baseline)	-1 to -90 days	-2 to -40 days	Day 0	Week 1 +/- 3 days	Week 2 +/- 3 days	Week 4 +/- 1 week	Week 8 +/- 1 week	Week 24 +/- 1 week
Informed Consent and Inclusion/Exclusion	X							
Urine Pregnancy Test <small>*females of child bearing potential only</small>	X							
Randomization	X							
Medical/Dental History	X							
X-rays (if none have been taken in the past two years)	X							
Oral Examination	X			X	X	X	X	X
Pain Visual Analog Scale (VAS)	X	X	X	X	X	X	X	X
Clinic Assessments*	X				X	X	X	X
Intraoral Photographs	X	X ~	X	X	X	X	X	X
Dental Impressions	X							
Tissue Harvest Biopsy ~		X ~						
Graft Placement			X ∞					
Graft Biopsy						X		
Laser Doppler Flowmetry (LDF)					X	X	X	X
Laboratory Evaluations +						X		
Assess Adverse Events		X	X	X	X	X	X	X
Follow-up phone calls will occur at 9 and 12 months post-grafting.								

\*Clinic assessments may include: PPD, CAL, BOP, Mobility, keratinization, graft contracture, graft color, wound healing index,

~Harvest biopsy will be performed only on subjects randomized to the experimental EVPOME arm of the study

+Laboratory evaluations include: histology, immunohistochemistry

∞At this time the POM graft will be harvested from the donor palatal site and grafted to the recipient site

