### 9.3 Sample Size and Accrual

We propose to have 60 subjects to give clinical and histological endpoints of interest at the primary assessment time of 4 weeks post graft. We expect no more than 6 subjects to potentially drop out of the study before providing Week 4 data, and thus will enroll 66 patients in total. With an estimated enrollment of 1 out of 5 screened patients, we expect to have a pool of over 330 patients over two years from which to select 66 subjects (33 subjects per group over two years) that will be randomized equally to one of the two groups - EVPOME and POM grafts. The randomization list will be prepared electronically in advance by the biostatistician and transferred to the MICHR statistics group for incorporation into the TATUM system. Randomization will be stratified by smoking status.

The primary clinical endpoint is the degrees of keratinized tissue. Secondary outcomes are contracture and wound healing index. Ancillary endpoints include the presence or absence of a continuous epithelial layer, the degree of vascular ingrowth, the LDF measurement of gingival blood flow. The main aim is to show that EVPOME treatment give comparable clinical and histological results when compared with POM treatment. It is also expected that the EVPOME will cause less patient discomfort and pain, and have a better color rendition to the surrounding tissue than the POM. Hence, we expect EVPOME to show better outcomes for pain, color rendition, and microvessel infiltration than POM, while showing comparable outcomes on primary endpoints of keratinized tissue and graft contracture or histological endpoints compared with POM. Sample size is calculated to show near equivalence of the two groups for primary and secondary outcomes. Sample size calculation and power consideration are provided following the data analytic plan described for each outcome.

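### Block sizes of 2, 4 or 6, printed in the protocol of a single-site trial with no masking described, could let a recruiter who tracks assignments guess up to about 70% of them (50% by chance)

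*Combined protocol and SAP*

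**What the plan says.** **Allocation.** Section 4.3 says: "The randomization schedule will begin with block sizes of 2, 4, or 6". It does not give the probability of each size, what follows the opening blocks, or any step to keep the sizes from recruiters. Section 3 gives the total and ratio: "A total of sixty subjects will be randomized in a 1:1 ratio to autogeneous EVPOME vs. POM". Section 9.3 plans 66 instead, to allow for losses: "We expect no more than 6 subjects to potentially drop out of the study before providing Week 4 data". It also adds a stratification that Section 4.3 does not mention: "Randomization will be stratified by smoking status". Since Section 4.2 excludes "Smoking or use of tobacco products within 6 months prior to screening", the strata can at most be never and former smokers.

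**Who can see past assignments.** Section 3 describes one centre: "This safety and efficacy study will be a single site, randomized, parallel-group". Section 4.3 says: "Upon randomization, an email will be sent to the Co-Investigator and/or any appropriate study staff". The arm is also evident from the visits, because under the schedule in Section 6.1 "Harvest biopsy will be performed only on subjects randomized to the experimental EVPOME arm of the study", and Section 6.2.1 sends POM subjects straight to Visit 3. No masking of staff or assessors is described. Section 6.2.1 has study staff at the clinic do the screening and consenting, and periodontics faculty do the recruiting.

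**Safeguards.** The biostatistician prepares the list in advance for the TATUM web system (Section 9.3). Assignment comes after consent and confirmed eligibility, and reasons for ineligibility and nonparticipation are recorded (Section 4.3).

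**The concern.** Holding the list centrally stops anyone reading the next assignment. It does not stop anyone predicting it from the assignments already made. With short balanced blocks at one site, the arm that is behind is the more likely next one, and the staff who screen can know which arm that is.

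Acting on a guess needs some latitude over who enters and when. The plan leaves some: one exclusion rests on the investigator's opinion (Section 4.2), about 1 in 4 or 1 in 5 screened subjects is enrolled (Sections 9.1 and 9.3), and randomization numbers follow the order in which subjects qualify (Section 4.3). Sites with up to 3 mm of keratinized mucosa are eligible, so starting widths can differ by more than the 0.55 mm margin. The primary analysis in Section 9.5 is a test of Week 4 means with no baseline adjustment specified. If more favourable sites went to one arm, even unconsciously, the shift would enter the primary comparison.

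**Working it through.** **1. The plan's own figure.** Inputs from Section 9.5, Aim 1: SD 0.65 mm, 30 per arm, two-sided 95% interval, margin 0.55 mm.
- SE = 0.65 × √(2/30) = 0.168 mm (plan: 0.17).
- Margin of error = 1.96 × 0.168 = 0.329 mm (plan: about 0.33).
- Equivalence power at no true difference = 2Φ(0.55/0.168 − 1.96) − 1 = 81.2% (plan: at least 80%).

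These reproduce. The documents give no figure for predictability.

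**2. Correct guesses.** The rule is to guess the arm that is behind and toss a coin when the arms are level. It needs no knowledge of the block sizes. Expected correct guesses in a block of 2b are b + ½(4^b / C(2b,b) − 1):
- size 2: 1.5 of 2 (75%)
- size 4: 2.833 of 4 (70.8%)
- size 6: 4.1 of 6 (68.3%)

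With equally likely sizes (an assumption), the long-run rate is (1.5 + 2.833 + 4.1)/12 = 70.3%. Simulated lists of 60 give 70.1%, and lists of 66 give the same. Size weights of 1:2:1, 3:2:1 and 1:2:3 (for 2:4:6) give 70.2%, 71.1% and 69.3%.

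**3. Stratification.** With two strata tracked separately the rate is 69.6%. Following only the pooled sequence gives about 64%, for a smaller stratum of 10% to 50% of subjects.

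**4. Near-certain assignments.** Here the guesser must know the possible sizes and their weights, and update optimally.
- Equal weights: 59% of all assignments are predictable with at least 75% certainty. The other weights in step 2 give 56%, 57% and 51%.
- Fully certain: about 4% with equal weights.
- At the start of the list, the second assignment differs from the first with probability (1 + 2/3 + 3/5)/3 = 0.756.

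**5. Possible effect on the primary comparison.** Assume each guess shifts the expected outcome by η, always in favour of EVPOME, for every subject. Then bias = 2η(2p − 1), where p is the correct-guess rate. False non-inferiority at a true deficit of 0.55 mm = 1 − Φ(1.96 − bias/0.168). The documents give no value for η, so 0.1 and 0.2 mm are assumed.
- p = 0.70, η = 0.1: bias = 2 × 0.1 × 0.40 = 0.08 mm; false non-inferiority 6.9%.
- p = 0.70, η = 0.2: bias = 0.16 mm; false non-inferiority 15.7%.
- p = 0.64, η = 0.2: bias = 0.112 mm; false non-inferiority 9.8%.

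With no steering the figure is 2.5%.

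**6. Alternatives (60 subjects, one list, equal weights).**

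| Scheme | Correct guesses | At least 75% certain | Fully certain | Bias at η = 0.2 mm | False non-inferiority |
|---|---|---|---|---|---|
| Blocks 2/4/6 | 70.1% | 59% | 4% | 0.16 mm | 16% |
| Blocks 4/6/8 | 67.8% | 35% | about 2% | 0.14 mm | 13% |
| Big-stick, maximum imbalance 3 | 58.0% | 16% | 16% | 0.06 mm | 6% |

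Under the big-stick rule, assignments are certain at the limit and 50:50 otherwise, so the two certainty columns coincide.

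**The case against.** The best defence is that the plan already has the main safeguards: a list prepared by the biostatistician, web assignment after confirmed eligibility, mixed block sizes and a log of reasons for ineligibility. Many exclusions are objective, and a patient's own request for surgery is not recruiter discretion. Section 9.5 allows adjustment, where appropriate, for graft area, geometry, age and general health, which could absorb part of any steering. All of this stands, and it lowers the risk. It does not prevent prediction from past assignments.

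Several stronger readings are tempting, but the documents do not support them:
- **That the second assignment of a block of 2 is known.** It is known only to someone who knows that the block has size 2. The sizes are mixed, and about 4% of assignments are fully certain.
- **That recruiters are told every assignment.** The email goes to the Co-Investigator and/or appropriate staff. Whether the recruiting faculty receive it is not stated.
- **That 70% is what would happen.** It is an upper figure for someone who tracks every assignment within stratum.
- **That the trial is stated to be open-label.** The absence of masking is inferred from the procedures and the lack of any description.
- **That no analysis could help.** Adjustment for baseline features or for the predicted assignment can reduce such a bias, though not reliably remove it.

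The contrast of 59% with 35% also depends on the cut-off. At 70% certainty, blocks of 2/4/6 and 4/6/8 both give about 59%. The benefit of larger blocks should therefore be described as modest.

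**Conclusion.** The concern holds as a weakness that should be corrected, not as evidence of bias. A recruiter who tracks assignments within stratum could guess up to about 70% correctly, against 50% by chance. That figure stays between 69% and 71% over the block-size weights tried, and it falls to about 64% if strata are ignored. The near-certainty figure of 51% to 59% is less firm, because it needs knowledge of the sizes and weights and optimal updating.

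A reader might infer that the false non-inferiority rate is 16%. The documents do not support that as an expected value. It requires an assumed 0.2 mm shift, full tracking, and every guess acted on in favour of EVPOME. Over assumed shifts of 0.1 to 0.2 mm the range is about 7% to 16%, from bias of about 0.08 to 0.16 mm. The latitude to steer exists; its use is not shown.

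**What to change.** Delete block size 2. Have the biostatistician generate the TATUM list with randomly ordered blocks of 4, 6 and 8 within smoking stratum. Take the sizes out of the site protocol, leaving only a statement that block sizes vary and are withheld from site staff. Record the sizes, their selection probabilities and the stratification in a restricted randomization document.

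The cost is one new list before enrolment, or for the remaining subjects if enrolment has begun. Imbalance could reach 4 per stratum, against 3 with a block of 6. In the worst case of two strata both off by 4 in the same direction, the arms would be 34 and 26. The SE would then be 0.65 × √(1/34 + 1/26) = 0.169 mm instead of 0.168 mm, and equivalence power about 80% instead of 81%.

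A big-stick rule with maximum imbalance 3 is an option to weigh, not a clear improvement. It lowers average guessing to 58%, but makes about 16% of assignments fully certain against about 4% now.

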## 5. STUDY INTERVENTIONS

### 5.1 Interventions, Administration, and Duration

#### 5.1.1 Oral Examination

Study investigators will examine the subject as part of a comprehensive oral examination to evaluate the mouth, jaw, and teeth to assure that there is no cancer

recurrence and to verify the absence of other pathology that would mitigate subject study inclusion (i.e. dental infection).

#### 5.1.2 Intraoral Photographs

Study staff, or medical residents aiding study staff will collect intraoral photographs for each subject randomized. Photographs will be taken of the graft site at a standard magnification (1:1 ratio) so that they can be compared from visit to visit to assess percent keratinization and contracture.

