### 5.1.6 Assessment of Graft Contracture

At each follow-up visit, the percent (%) graft contracture will be determined by linear measurements taken from the periphery of the standardized size graft.

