#### 6.3.6 Laboratory Evaluations

Histology and immunohistochemistry evaluations will be performed on tissue collected via the Visit 6 biopsy. Histology will consist of standard hematoxylin and eosin stains to assess presence and maturity of the epithelial layer, while immunohistochemistry will assess the endothelial cells in microvessels within the dermal component.

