## 9.2 Outcomes

### 9.2.1 Primary outcome

The primary outcome will be clinical increase in zone (width) of keratinized mucosa (KM). For edentulous sites, KM width will be measured by determining the distance from the crest of the edentulous ridge to the mucogingival line to the nearest millimeter with a Castroviejo caliper. For patients with an existing implant or tooth, KM width will be measured from the implant mucosal or tooth margin to the mucogingival line.

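### No masked reading is specified for the Week 4 slides or the graft photographs, although both could be coded with material already collected

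*Combined protocol and SAP*

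**What the plan says.** **Photographs.** Section 5.1.2 says "Study staff, or medical residents aiding study staff will collect intraoral photographs for each subject randomized", at a fixed magnification, "so that they can be compared from visit to visit to assess percent keratinization and contracture". They are therefore a source of measurement as well as a record. No reader is named. Section 9.5 does not say whether a photograph value or a chairside value enters the contracture analysis.

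**Slides.** Section 6.3.6: "Histology and immunohistochemistry evaluations will be performed on tissue collected via the Visit 6 biopsy". Section 9.5 (Ancillary Outcomes) uses two readings from that biopsy: whether a continuous epithelial layer is present, and an ordinal microvessel grade from 1 to 4. No reader is named here either.

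**Knowledge of the arm.** Section 4.3: "Upon randomization, an email will be sent to the Co-Investigator and/or any appropriate study staff". No limit is placed on who may know the assignment. The arms also follow different paths. A footnote to Section 6.1 says "Harvest biopsy will be performed only on subjects randomized to the experimental EVPOME arm of the study", and under Section 5.1.6 (Biopsy and Specimen Handling) that specimen goes to the manufacturing laboratory labelled with the subject study number.

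**Expected result.** Section 9.1 puts superiority on microvessel infiltration into the primary hypothesis. Section 6.2.6 says that more microvessels and earlier epithelial maturity are expected with EVPOME.

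**Chairside measurements.** For edentulous sites, Section 9.2.1 measures KM width from the ridge crest "to the mucogingival line to the nearest millimeter with a Castroviejo caliper". Under Section 5.1.6 (Assessment of Graft Contracture), "the percent (%) graft contracture will be determined by linear measurements taken from the periphery of the standardized size graft".

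**The concern.** The surgeon and the patient can hardly be masked when one arm has a palatal graft harvested at surgery and the other has a punch biopsy weeks before. Slides and photographs are different. They can be separated from the patient, given a code, and read by someone who is not told the arm. The plan does not use that opportunity.

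The microvessel grade matters most. It is a subjective four-point score, the protocol has stated which arm should do better, and superiority on it is part of the primary hypothesis. A reader who knows the arm and the expectation may settle borderline slides in one direction, and nothing in the plan would reveal it. The photographs offer a second benefit: a coded reading would give an independent check on contracture, and possibly on KM change, where the chairside examiner may know the arm.

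**Working it through.** **1. Is any reading masked?**

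| Reading | Where | Type | Masking stated | Can be coded afterwards? |
|---|---|---|---|---|
| Continuous epithelium, Week 4 | 9.5, 6.3.6 | Slide, yes/no | None | Yes |
| Microvessel grade, Week 4 | 9.5, 6.3.6 | Slide, 1 to 4 | None | Yes |
| Percent keratinization and contracture from photographs | 5.1.2 | Image | None | Yes |
| KM width (primary) | 9.2.1 | Chairside | None | No |
| Linear contracture | 5.1.6, 6.2.5 | Chairside | None | No |
| Wound Healing Index, graft color | 9.2.2, 9.2.3 | Chairside | None | No |
| Laser Doppler flowmetry | 6.2.5 | Instrument | None | No |
| Pain | 9.2.3 | Visual analog scale | None | No |

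The first three rows are the point. The other five lie outside it.

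**2. Does study ID labelling already mask the slides?** Section 11.2 puts only the study ID on material leaving the site, for confidentiality. The number is assigned before randomization (Section 4.3), so it does not encode the arm. But harvest specimens exist only in the EVPOME arm and carry the same subject number. Anyone with the manufacturing or assignment records can link number to arm, so a separate code is needed.

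**3. Size for the microvessel grade.** Inputs from Section 9.5: SD 1, 30 per arm, two-sided 0.05 test.

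- SE = 1 × √(2/30) = 0.258. Margin of error = 1.96 × 0.258 = 0.51, as stated.
- Power at a difference of 0.72 = Φ(0.72/0.258 − 1.96) = 80%, as stated.
- Chance of a false finding in favour of EVPOME when the arms are equal and its mean grade is read too high by b: Φ(b/0.258 − 1.96).

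The values of b are my assumption, since the documents give none. I express them as the number of the 30 EVPOME slides raised by one grade, taking a higher grade to mean more vessels.

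| Slides raised | b | Chance |
|---|---|---|
| 0 | 0 | 2.5% |
| 3 | 0.1 | 5.8% |
| 6 | 0.2 | 12% |
| 9 | 0.3 | 21% |

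**4. Size for the primary outcome, for context only.** Inputs from Section 9.5, Aim 1: SD 0.65 mm, 30 per arm, margin 0.55 mm.

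- SE = 0.65 × √(2/30) = 0.168 mm (stated 0.17). Margin of error = 1.96 × 0.168 = 0.33 mm, as stated.
- Probability that the 95% interval lies within ±0.55 mm when the true difference is 0: 2Φ(0.55/0.168 − 1.96) − 1 = 81% (stated at least 80%).
- If EVPOME is truly 0.55 mm worse and readings lean toward it by b mm, false non-inferiority has probability Φ(b/0.168 − 1.96): 2.5% at b = 0, 8.6% at 0.1 mm, 22% at 0.2 mm.

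These shifts are also assumed. They act on the chairside reading, which coding slides and photographs does not mask.

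**The case against.** **Most efficacy outcomes are not read from slides or images.** A reader might infer that every efficacy outcome is exposed through this gap and that closing it protects them all. The documents do not support that. KM width, linear contracture, Wound Healing Index and graft color are assessed on the patient, laser Doppler flowmetry is an instrument reading, and pain is a visual analog scale. The slides feed only outcomes that Section 9.2.3 calls ancillary. This stands and limits the point.

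**The 8.6% and 22% are not a risk that the fix removes.** They describe a lean in the chairside reading. Nor does rounding to 1 mm favour either arm by itself, and the Synopsis also mentions a probe read to 0.5 mm. This stands too.

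**Silence is not proof.** The documents do not say that readers will know the arm and do not describe the trial as open-label. Section 6.3.1 mentions a Manual of Procedures, which is not among the documents and might cover slide reading. What stands is that the protocol and analysis plan do not require masking, so they cannot be cited as assurance of it.

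**Coding may not hide the arm.** Sections 9.3 and 9.5 expect a difference in color, and the AlloPatch matrix might be recognisable on histology. Staff who saw the patient may recognise a photograph. The documents do not settle how much masking would survive, nor show that the mucogingival line can be read reliably from a photograph. This argues for using the photograph values as a sensitivity analysis only.

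**Conclusion.** The point holds in a limited form. The plan specifies no masked reading for the Week 4 slides or the graft photographs, the two sources that could be masked with what is already collected. The consequence is clearest for the microvessel grade, where a one-grade lean in 3 to 9 of 30 EVPOME slides would raise false superiority from 2.5% to between 5.8% and 21%. That range rests on the plan's SD of 1, a normal approximation and shifts that I assumed. It shows sensitivity and does not estimate actual bias. The planned sample size and error rates are unaffected.

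The finding does not extend to the chairside outcomes, laser Doppler flowmetry or pain. It also does not show that any reader will in fact know the arm.

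**What to change.** - **Slides (Sections 5.1.7, 6.3.6 and 9.5).** Label the Week 4 slides with a random code in place of the subject number. Whoever is assigned to read them scores them in random order, and scores are locked before the code is opened. Someone who does not read slides holds the code list.
- **Photographs (Section 5.1.2).** Do the same for the Visit 1 (pre-graft), Visit 3 and Visit 6 images. State that the Visit 3 image is taken after graft placement, since Section 6.2.3 does not say. The Visit 1 image is needed for KM change, and the Visit 3 image for contracture. Visit 8 is left out because Section 6.2.8 makes that photograph discretionary, although Sections 6.1 and 6.3.7 schedule it.
- **Analysis (Section 9.5).** Name the chairside measurement as the analysed value. Pre-specify the coded photograph contracture, and KM change where the landmarks can be read, as a sensitivity analysis beside it.
- **Reporting.** State that chairside outcomes, laser Doppler flowmetry and pain were not masked by this step.

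The cost is relabelling, keeping a code list, and the time to measure coded photographs. No visit, procedure or additional subject is needed. The downside is that masking may be only partial.
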